### 12.2.1 Severity

The generic categories below are given for use as a guide. You may have a more specific scale that you want to use related to the disease (e.g. CTCAE criteria), amend as required.

Category	Definition
Mild	The adverse event does not interfere with the participant's daily routine, and does not require further intervention; it causes slight discomfort
Moderate	The adverse event interferes with some aspects of the participant's routine, or requires further intervention, but is not damaging to health; it causes moderate discomfort

Severe	The adverse event results in alteration, discomfort or disability which is clearly damaging to health
--------	---

## 12.2.2 Causality

The assessment of relationship of adverse events to the intervention is a clinical decision based on all available information at the time of the completion of the case report form. The differentiated causality assessments will be captured in the trial specific AE Log and/or SAE form. The following categories will be used to define the causality of the adverse event:

Category	Definition
Related	A causal relationship between the intervention and an adverse event is at least a reasonable possibility, i.e., the relationship cannot be ruled out.
Not related	There is no reasonable possibility of a causal relationship between the intervention and an adverse event.
Not Assessable	Unable to assess on information available.

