### ***“Real-world testing” cycle***

This testing cycle will involve evaluating the prototype intervention with a staff participant and a service user participant. The staff participant will receive the intervention and any training resource in advance of the testing.

Staff participants will identify service users they work with who meet the sampling criteria (Section 5.1.1). If a service user agrees to participate, they will be consented either together with the staff participant or separately. If both parties are agreeable, the testing session may be recorded; this recording is optional.

The follow-up interviews can take place immediately after the intervention or on a later date, depending on what can be arranged. Staff and service user participants will be interviewed separately to ensure free expression of their views. If both parties agree and it is practical, a joint interview may also be conducted. All interviews will be recorded and will focus on engagement, usability, and the value of the intervention, as well as suggestions for improvement.

As part of user testing, minor refinements to the intervention will be made after each testing session, while more complex adjustments will be undertaken in consultation with the research team.

Following the completion of WP3, interview recordings and field notes will be reviewed to refine a logic model, describing the key components of the intervention, contextual factors affecting how it is delivered, its perceived impacts and the mechanisms by which they are achieved. Together with a description of the iterative development of the intervention will be written up as an academic paper.

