## 11. ASSESSMENT AND MANAGEMENT OF RISK

The table below summarise the risks and mitigations for testing the intervention above standard care that are being performed in a table:

Intervention	Potential risk	Risk Management
Interview of service user participants WP1	There may be a small possibility that the service user participant will get upset or emotionally distressed whilst taking part in the interviews and testing of intervention.	
What the study involves will be clearly explained to participants in the study information sheet and by researchers, and written informed consent will be received before participants join the study.
 
The interview topic guides will be developed with the study Lived Experience Advisory Panel (LEAP) that will consist of people with lived experience of MHA assessment.
 
If participants become distressed the study researcher will use their skills to make sure the participant feels as safe as possible. The lead researcher LB is an experienced mental health worker and has expertise in dealing with distress. The researchers will use guidance from sensitive subject research. This will include monitoring the participants' mental state, offering breaks, offering the opportunity to talk through their difficulties (if they want to), providing a safe and containing environment to conduct the research and ensuring a person-centred stance is taken. A distress protocol will be developed with the LEAP group to guide if a participant becomes upset.
 
A debriefing time will be offered after to discuss any emotions and questions raised in the interview and this time was viewed as valuable in a previous study.
 
Service user participants will be given a sheet with local and national support services for mental health (see Support Resources Sheet) for them to use after the interview if needed. We will also provide information on MHA assessments which the LEAP will develop.
 
For WP1, the participants will be asked to provide details of a support person- mental health worker, friend or family who they can talk to after if needed. Contact details will be requested at beginning of interview.
 
In the unlikely event that the participant becomes distressed, and it is not manageable by the researcher, will also contact their support person if there is concern that they are at a risk to themselves, or self-harming intent/suicide is disclosed. Each participant will be given a list of contacts if feeling any distress following the interview

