## 12.2 Assessments of Adverse Events

WP1 and WP2 involve one-off interviews and stakeholder meetings, with no intervention. We do not propose to formally monitor SAEs in these phases of the study.

WP3 involves clinical staff using our novel intervention with six service user participants. It is possible in theory that service users could experience the intervention negatively and this could result in a serious adverse event. We will monitor SAEs in WP3 through feedback from the involved clinical and service user participants at the time of the intervention and in the follow-up interview.

In addition to SAE monitoring, we will also keep a Harms Log, recording any reported negative experiences of the interviews or intervention across all three Work packages. We will report the nature of the harm, which participant was affected, action taken to resolve the harm, and any actions planned to prevent recurrence. This harms log will be reviewed at least monthly by LB and her clinically qualified supervisors SJ and BLE, and by the wider project management group (see 15.2) at scheduled meetings. It will be available for review by the sponsor as requested. For this study, there will only be Adverse Events and Serious Adverse Events for work package 3.

Each adverse event (AEs) will be assessed for severity, causality, seriousness and expectedness as described below.

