## 12.2.3 Expectedness

All SAEs assigned by the Investigator or delegate as suspected to be related to the intervention will be assessed for expectedness against as outline below. No AEs or SAEs are expected because it is a one-off intervention testing.

Category	Definition
Expected	An adverse event which is consistent with the information about the intervention listed in the current SmPC, Manual of Operation (amend as appropriate) or clearly defined in this protocol.

Unexpected	An adverse event which is not consistent with the information about the intervention listed in the current SmPC, Manual of Operation (amend as appropriate) * or clearly defined in this protocol.
-------------------	--

\* *This includes listed events that are more frequently reported or more severe than previously reported.*

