#### 12.3 Procedures for recording and reporting Serious Adverse Events (SAEs)

All serious adverse events will be recorded in the medical records and the CRF, and the sponsor's AE log. The AE log will be reported to the sponsor at least once or twice per year and reviewed by the Project Management Group.

Where the event is unexpected and thought to be related to the intervention, this will be reported by the Investigator to the Health Research Authority within 15 days.

Completed SAE forms must be sent within 5 working days of becoming aware of the event to the Sponsor Email **forms to [[contact]](mailto:[contact])**

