# 13. OVERSIGHT COMMITTEES

## 13.1 Trial Management Group (TMG)

LB's PhD thesis committee will act as the Project Management Group (PMG) and the roles of the Trial Management Group for this study. The PMG will include the Chief Investigator (BLE), LB, SJ, qualitative expert [name] (NM), other academics with method or subject expertise for the work package, representative from the Lived Experience Advisory Panel. The PMG will be responsible for overseeing the trial phase (WP3) and the whole study. It will meet at least 6 monthly throughout the study. It will provide independent oversight and advice on all work packages and ensure protocol and ethics procedures being adhered to. The PMG will review recruitment figures, SAEs and substantial amendments to the protocol prior to submission to the REC. All PIs will be kept informed of substantial amendments through their nominated responsible individuals. The PMG will advise on development of the study intervention and trial procedures. The PMG will also review adverse events thought to be linked to the study or other concerns regarding the safety of the trial.

This PMG will act as the Trial Management Group for the testing work package (WP3) of the study. The PMG will review recruitment figures, SAEs and substantial amendments to the protocol prior to submission to the REC. As there will be more regular meetings between the CI and lead researcher LB then monthly supervision meetings will also complete this role (see 13.2). All PIs will be kept

informed of substantial amendments through their nominated responsible individuals. The PMG will monitor data collection and there is no separate Data monitoring committee.

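### Relatedness and the 15-day report refer only to the intervention, so a WP3 SAE attributed solely to a research interview would be coded unrelated and fall outside that report

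*Protocol*

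**What the plan says.** Section 12.2.2 defines causality by one reference. *Related* means "A causal relationship between the intervention and an adverse event is at least a reasonable possibility, i.e., the relationship cannot be ruled out", and *Not related* means "There is no reasonable possibility of a causal relationship between the intervention and an adverse event". The third category, *Not Assessable*, is for events that the available information does not allow to be judged.

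Two later rules use the same reference. Section 12.2.3: "All SAEs assigned by the Investigator or delegate as suspected to be related to the intervention will be assessed for expectedness". Section 12.3 sets a 15-day limit for informing the Health Research Authority, on this condition: "Where the event is unexpected and thought to be related to the intervention, this will be reported by the Investigator".

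Other parts of the protocol are wider. The Harms Log in Section 12.2 takes in bad experiences of interviews as well as of the intervention, in all work packages. Section 13.1 says "The PMG will also review adverse events thought to be linked to the study or other concerns". The risk table in Section 11 foresees that a service user may "get upset or emotionally distressed whilst taking part in the interviews and testing of intervention", although that row is labelled for the WP1 interview.

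The real-world testing cycle in Section 7.1.1 has staff and service users interviewed separately, either straight after the session or on another day, and adds: "If both parties agree and it is practical, a joint interview may also be conducted". All interviews are recorded; recording of the testing session is optional.

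**The concern.** The protocol recognises that a research interview can cause harm, but its causality definition has no place for that cause. The definition also controls external reporting, because the 15-day rule applies only to events thought related to the intervention. An event that the assessor traces to the interview and not to the intervention therefore receives a code suggesting that the research played no part, and the 15-day report is not triggered. At stake is the attribution of a serious event in a small test whose purpose is to find problems before a larger study.

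**Working it through.** No arithmetic applies: the protocol has no statistical section, and the only figures here are stated time limits. The check is to follow one event through the rules.

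**Is the interview part of the intervention?** No.
- Section 6.1 describes the intervention as a structured conversation led by clinical staff.
- Section 7.1.1 times the interview relative to the intervention and allows it on a later date, so the two are distinct.
- Section 7.2 names testing and the interview that follows as two things consented to.
- Section 12.2 says that the interviews and meetings of WP1 and WP2 involve no intervention. The column heading *Intervention* above the WP1 interview row in Section 11 therefore does not bring interviews into the causality definition.

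**Case A: interview straight after the session.** *Not related* requires that no reasonable possibility of a link to the intervention remains. With session and interview back to back, an assessor will often be unable to exclude the session. The code is then *Related* or *Not Assessable*. If it is *Related*, the remaining condition is that the event is unexpected, and Section 12.2.3 states that no events are expected. The 15-day report is then due.

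**Case B: interview on a later date, event attributed to the interview, intervention ruled out.**
1. Section 12.2.2: no reasonable possibility of a link to the intervention, so *Not related*.
2. Section 12.2.3: not suspected to be related to the intervention, so not sent to the expectedness check.
3. Section 12.3: not thought related to the intervention, so the 15-day condition is not met.

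**What still happens in Case B.**
- Section 12.3: entry in the medical records, the CRF and the AE log, and an SAE form to the Sponsor within 5 working days, whatever the causality code.
- Section 12.2: Harms Log entry, reviewed at least monthly by the lead researcher and clinically qualified supervisors.
- Sections 13.1 and 13.2: SAE review by the Project Management Group and in monthly supervision.

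**Expectedness.** Section 12.2 says "Each adverse event (AEs) will be assessed for severity, causality, seriousness and expectedness as described below". Section 12.2.3, to which this leads, limits the check to SAEs suspected to be related to the intervention. The two differ in scope. The 15-day gap does not depend on which governs, because Section 12.3 sets its own condition of relation to the intervention.

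**The case against.** The strongest reply is that the threshold for *Related* is low. The WP3 interview is about the intervention, covering its usability and value, and Section 7.1.1 intends interviewing to follow testing closely. An assessor could seldom exclude the intervention as a contributor. This stands, and it limits the point to Case B. A reader might infer that every SAE arising around a WP3 interview has to be coded *Not related*; the *Related* definition and the *Not Assessable* category do not support that.

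A second reply is that losing the expectedness check costs little, since Section 12.2 claims that check for every adverse event and Section 12.2.3 expects none. This also stands. The practical loss lies in the 15-day report.

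A third is that interview harm is already logged, reviewed and sent to the Sponsor. That is correct. A reader might go further and infer that the WP3 safety summary would understate harm from the study, but nothing in the protocol says that harm will be summarised from causality codes alone. Nor would counting how many WP3 contacts are interviews size the problem: it would measure exposure, not the chance of an SAE.

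Finally, the Section 11 wording sits in a WP1 row, and Section 13.1 sets a review remit, not a causality definition. Neither strictly contradicts Section 12.2.2. They show that the protocol elsewhere counts harm from research procedures, which is enough to make the narrower definition worth correcting.

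**Conclusion.** The point holds in a narrow form. A WP3 SAE attributed solely to a research procedure, most plausibly a separate or joint interview held on a later date, with the intervention ruled out, would be coded *Not related* and would not trigger the 15-day report. The loss is correct attribution and that report; the event itself is not hidden.

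At most six service users take part in real-world testing. The protocol gives no SAE rate, so no probability can be attached, and it is likely to be low. The conclusion assumes that the definitions are applied as written and that the interview is not treated as part of the intervention.

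One qualification applies to the Sponsor safeguard. Section 12.4 keeps SAE reporting to the Sponsor open until the end of the trial, which Section 7.3 sets at the last participant's last testing session. A later interview with that participant could fall after this date.

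**What to change.** In Sections 12.2.2, 12.2.3 and 12.3, replace the intervention as the causality reference with: the intervention or a WP3 research procedure (recording, separate or joint follow-up interview). Add a field to the AE log and the SAE form for which of the two is the suspected cause, so that events due to the intervention can still be told apart when it is refined. Reconcile Section 12.2, which has every adverse event assessed for expectedness, with the narrower rule in Section 12.2.3.

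The cost is wording in these subsections and one field on two forms. The downside is that slightly more events may be coded related and need a 15-day report.

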## 12.2.3 Expectedness

All SAEs assigned by the Investigator or delegate as suspected to be related to the intervention will be assessed for expectedness against as outline below. No AEs or SAEs are expected because it is a one-off intervention testing.

Category	Definition
Expected	An adverse event which is consistent with the information about the intervention listed in the current SmPC, Manual of Operation (amend as appropriate) or clearly defined in this protocol.

Unexpected	An adverse event which is not consistent with the information about the intervention listed in the current SmPC, Manual of Operation (amend as appropriate) * or clearly defined in this protocol.
-------------------	--

\* *This includes listed events that are more frequently reported or more severe than previously reported.*

#### 12.2.4 Recording of Adverse Events

All adverse events will be recorded in the medical records in the first instance.

All Adverse events will be recorded in the CRF following consent.

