## 9. DATA MANAGEMENT

### 9.1 Confidentiality

The study is compliant with the requirements of the General Data Protection Regulation (2016/679) and the UK Data Protection Act (2018). All Investigators and study site staff will comply with the requirements of the General Data Protection Regulation (2016/679) with regards to the collection, storage, processing and disclosure of personal information, and will uphold the Act's core principles. UCL is the data controller; the UCL Data Protection Officer is [name] ([[contact]](mailto:[contact])). The data processors are UCL research team and NHS staff.

Personal Data will be collected directly from participants and no data from the medical record systems by the UCL research team.

The study will be collecting the following personal data:

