## 9.2 Data collection tools and source document identification

Data will be collected from participants by the research team and will be recorded specific case report forms (CRFs) or data collection tools such as electronic CRFs.

Where participant data is collected remotely through videocalls, we will leave a file note on the CRF documenting where (on the UCL Data Safe Haven) the audio-recorded data are stored. Similarly, any paper copies of forms (e.g. consent and demographic forms) location will also be recorded on CRF.

In this study, there is little source data and documents like the demographic information will be transcribed onto the CSF.

A source document list will be implemented prior to the start of the trial to identify:

- which data is to be recorded directly onto the CRF.
- which data is recorded firstly into source documents, such as medical notes, and then transcribed into the CRF; and
- which data is not to be recorded in the CRF but only recorded in source documents, e.g. participant questionnaires.

It is the responsibility of the investigator to ensure the accuracy of all data entered in the CRFs. After the delegation log will identify all those personnel with responsibilities for data collection and handling, including those who have access to the trial database.

For this study the data contained in CRF will be only taken from the participants and probably include the following:

- Demographic information and diagnosis
- Basic information about experience of MHA assessments, outcomes and other mental health history
- Roles and profession
- Type of consent given either on paper or an audio file for online.
- Who interviewed or which focus group attended (WP1)/ Workshop attended (WP2)/ Test session (WP3) with whom
- If any distress/ emotional response experienced in the interview
- Any adverse events
- Any details of the support plan agreed by the research team member and the participant.

**Transcripts of Interviews and Focus Groups (WP1 and WP2)** After the interviews and focus group data are transcribed, then the lead researcher LB will fully anonymise them through removing any direct or indirect personal identifiable details, for example, mention of named hospital or teams. Fully anonymised versions of the transcripts will be analysed using NVivo software and saved on UCL online drives with access limited to the research team, including Lived Experience Researchers (LEAP members) and the supervisory team.

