## 9.3 Completing Case Report Forms

For this study, the CRF will be completed by the UCL research team and will be stored immediately on UCL Data Safe Haven electronically.

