## 12. RECORDING AND REPORTING OF ADVERSE EVENTS

### 12.1 Definitions

Term	Definition
Adverse Event (AE)	Any untoward medical occurrence in a patient or trial participant, which does not necessarily have a causal relationship with the intervention involved.
Serious Adverse Event (SAE).	Any adverse event that: 
 
• results in death,
 
• is life-threatening*,
 
• requires hospitalisation or prolongation of existing hospitalisation**,
 
• results in persistent or significant disability or incapacity, or
 
• consists of a congenital anomaly or birth defect.
 
• Other ‘important medical events’ may also be considered serious if they jeopardise the participant or require an intervention to prevent one of the above consequences
 

\* A life-threatening event, this refers to an event in which the participant was at risk of death at the time of the event; it does not refer to an event which hypothetically might have caused death if it were more severe.

\*\* Hospitalisation is defined as an in-patient admission, regardless of length of stay. Hospitalisation for pre-existing conditions, including elective procedures do not constitute an SAE.

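### WP3 fixes no active follow-up for harm after the follow-up interview and names no one to carry events from the medical record to the study

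*Protocol*

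**What the plan says.** **Where events are recorded.** Protocol Section 12.2.4 consists of two statements: "All adverse events will be recorded in the medical records in the first instance", and "All Adverse events will be recorded in the CRF following consent". Section 12.3 adds that each SAE goes into the medical records, the CRF and the sponsor's AE log, with the SAE form due at the Sponsor five working days after awareness.

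**Where CRF data come from.** Section 9.3 says "the CRF will be completed by the UCL research team". Section 9.2 says "For this study the data contained in CRF will be only taken from the participants", and the list that follows includes adverse events. Section 9.1 says "Personal Data will be collected directly from participants and no data from the medical record systems by the UCL research team".

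**When SAEs are sought.** Section 12.2 relies on feedback from the staff and service user participants "at the time of the intervention and in the follow-up interview". On the timing of that interview, Section 7.1.1 (real-world testing) says "The follow-up interviews can take place immediately after the intervention or on a later date". No minimum or maximum interval is given.

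**How long reporting lasts.** Section 12.4 has SAEs reported to the Sponsor up to the end of the trial. Section 7.3 sets that end at the final WP3 participant's last testing session.

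**What counts.** A footnote in Section 12.1 says "Hospitalisation for pre-existing conditions, including elective procedures do not constitute an SAE".

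**What else exists.** Sections 11 and 12.2 set up a harms log, fed by what the service user or clinical team tells the study and reviewed at least monthly.

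**The concern.** Section 12.2 itself accepts that a service user could experience the intervention badly and that an SAE could follow. The people exposed have had a Mental Health Act assessment within the past year (Section 5.1.5). Distress, deterioration or admission in the days after the conversation is the kind of harm the plan should be able to see.

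As written, the plan asks about harm at two moments that may fall on the same day, and sends the first record of any event to a place the research team does not read. A count of no SAEs from WP3 could then mean either that none occurred or that nobody asked after the session day. The reader of the results could not tell which, and Section 20.1 intends the outputs to lead quickly to a feasibility and pilot study.

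**Working it through.** The protocol has no statistical design (Section 10) and states no figure to reproduce, so the check sets the passages side by side.

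**Step 1: the route from record to CRF.** Section 12.2.4 requires both entries but does not say who makes either. Section 9.3 gives the CRF to the UCL team. Section 9.1 keeps that team out of the record systems, and Section 9.2 limits CRF content to what participants supply. An event known only from the record therefore has no stated path to the CRF. A general line in Section 9.2 foresees some data being copied from medical notes into the CRF; that conflicts with Section 9.1 and with the participant-only statement in the same section. Section 9.4 says NHS staff also collect data, but gives them no adverse event task.

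**Step 2: the time windows.** Combining Sections 7.1.1, 7.3, 12.2 and 12.4 gives four cases:

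| Service user | Interview | Active questioning after the session | SAE reporting period after the session |
|---|---|---|---|
| Not the last tested | Immediate | None beyond the session day | Until the last participant's session |
| Not the last tested | Later | Until the interview, length not stated | Until the last participant's session |
| Last tested | Immediate | None beyond the session day | None beyond the session day |
| Last tested | Later | Until the interview, length not stated | None beyond the session day, so the interview falls outside it |

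The reporting period thus depends on the order of testing. In the last row, an SAE first disclosed at the interview lies outside the stated period.

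**Step 3: the passive routes.** The harms log covers what is reported to the study, and its monthly review looks at what has arrived. The staff participant is made responsible for continuing support (Section 11), but no section asks that person to notify the study after the interview. The five-day clock in Section 12.3 starts only once someone is aware. None of these creates an occasion on which anyone looks.

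**Step 4: Appendix 1.** It lists adverse event reviews up to Day 42, but it is an unedited template with randomisation, several visits and unfilled day numbers. It does not fit what Section 7.2 calls a single session, so it does not supply the missing follow-up.

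**Step 5: the footnote in Section 12.1.** In people recruited because of a recent Mental Health Act assessment, a psychiatric admission after the session would usually concern a condition that pre-dates it. Whether such an admission falls under the exclusion is left open.

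**The case against.** The strongest reply is that the plan does have a route for later harm. The harms log is expressly additional to SAE monitoring, names the clinical team as a source, is reviewed at least monthly, and can lead to the intervention phase being changed or paused. Sections 12.2.4 and 12.3 do require CRF and AE-log entry. Section 9.1 bars the UCL team from drawing on record systems; it does not stop a clinician telling the team about an event. NHS staff are named as data processors, and secure email between sites and the team is provided for. The WP3 clinician is a participant, so a report from that person fits the participant-only rule. Section 9.2 promises a source document list, and Section 15 a monitoring plan proportionate to risk.

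Most of this stands. A reader might infer that later events cannot reach the study, or that the session and interview are the only routes; the documents do not support either. What remains is that the additional routes are passive, that the required entries have no assigned reporter, and that no interval is fixed.

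Two other strong readings also go too far. No section says that a nil SAE count will be offered as evidence of safety: WP3 tests acceptability and usability in at most six people, and Section 20.3 disclaims evidence for roll-out before a further trial. Nor does Section 12.1 state that every psychiatric admission is excluded: the footnote is ambiguous, and the category of other important medical events remains available.

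**Conclusion.** The point holds as a gap in active ascertainment and in the hand-off of events. Followed exactly, the plan can involve no active search for harm after the session day, and for the last service user it closes SAE reporting on that day. Harm after the interview need not reach the study, although it may through the harms log or the care team.

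The size is up to six service users. How many events would be missed cannot be estimated: the documents give neither an event rate nor a pattern over time, and any percentage would rest on an invented window. The conclusion assumes only that the sections are applied as written and that the source document list and monitoring plan, which are not yet described, do not add a post-session check. This should be settled before WP3 opens.

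**What to change.** 1. In Sections 12.2 and 12.2.4, name the WP3 staff participant as reporter. At one fixed point after each session, that person returns a short AE/SAE form to the research team, including when there is nothing to report. The CI and Sponsor set the interval. Keep the harms log as the additional route.
2. Reconcile Sections 9.1, 9.2 and 12.2.4 on how an event in the medical record reaches the CRF. A return from the staff participant needs no access to records by the UCL team.
3. In Sections 7.3 and 12.4, move the end of trial and the SAE reporting period to the last follow-up contact.
4. In Section 12.1, state whether a new psychiatric admission after the session falls under the exclusion for pre-existing conditions.

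The cost is protocol and consent wording, since the staff member would be reporting on the service user, plus one short form per session. That is six forms if each service user has one session, as in Section 7.2. Section 6.1 anticipates one or two sessions; with two, it would be 6 × 2 = 12.
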